6.3 Randomization and Blinding

Randomization will be done according to a 1:1 ratio. The randomization scheme will be done using blocks of 10 so that for every 10 participants, 5 will be randomized to each group. A data manager ([name], MA) will generate the allocation sequence using the Microsoft Excel random number function. At study outset, each assignment for the full sample will be placed in sequentially numbered sealed envelopes. When participants show up for the initial training visit, the randomization envelope for that participant will be opened at which time the participant's randomized group will be revealed to the individual conducting the participant's training.

Participants will know which intervention they are assigned to (FOCAL+ or sham intervention) but will be blind as to which intervention was the active intervention (FOCAL+). Research assistants who implement the intervention will not be blind to participant randomization; however, research assistants who code the DriveCam data (onset and off set of eye glance duration and crashes/near crashes) will be blind to participant randomization.

6.4 Study Assessments

Frequency and Timing of Relevant Assessments:

	Baseline/Randomization	1-month follow-up assessment	6-month follow-up assessment	12-month follow-up
Diagnostic and Clinical Assessment	X			
Driving Simulation Assessment		X (2 runs)	X (2 runs)	
DriveCam Recording	X (Installation)	← CONTINUOUS →		
Driving Records		← CONTINUOUS →		
Adverse event monitoring		← CONTINUOUS →		

Analysis Time Windows:

Visit (target day)	Lower bound (days)	Upper bound (days)
Baseline/Diagnostic and Clinical Assessment (-7)	-14	-7
Randomization/Training 1 (0)	N/A	N/A
Training 2 (7)	4	10
Training 3 (14)	11	17
Training 4 (21)	18	24
Training 5 (28)	25	31
Month 1 (30 post-training 5)	30	45
Month 6 (180 post-training 5)	180	195
Month 12 (360 post-training 5)	Not in person	Not in person

Study Variables:

Primary Endpoint Variables Collected During Secondary Task (ST) Performance Portion of Driving Simulation:

1) Extended eye glances: This variable will be a frequency count of the number of ≥ 2 secs glances. Extended eye glances of interest are those occurring during the ST portions of the drive. The range for this variable could range from 0 to 100.

2) Standard Deviation of Lane Position (SLDP): Standard deviation of lane position will be calculated during the ST portions of the drive. An average of 0 indicates that an individual maintained consistent lane position. The range for this variable is from 0 to 3

Secondary Endpoint Variables Collected using DriveCam:

1) Extended eye glances: As has been done in previous research, the number of ≥ 2 sec eye glances away from the roadway occurring between -5 secs before to 1 sec after the event causing a .6 g-force will be calculated (Dingus, Klauer, Neale et al., 2006). For each event video, we will code the onset and offset of glances away from the roadway. Based on the onset and offset times, we will calculate whether the video clip contains a continuous eye glance away from the roadway that lasts for 2-seconds or longer between -5 secs before to 1 sec after the event. It is possible that some participants will not contribute any data at all to this outcome variable due to not experiencing any .6 g-force events during the 12-month observation. The lower end of the range for this variable for participants who do experience at least 1 .6 g-force event during the observation period is 0. There is no upper limit to this variable.

2) Crashes and near crashes (CNC): Like the extended eye glance endpoint, this variable is only calculated when participants experience a g-force event $\geq .6$. Coders will record whether the event captured a crash (i.e., contact between the vehicle and another object) or near crash (i.e., an evasive maneuver performed to avoid a MVC). Some participants may not contribute data due to not having any events. These participants will not be included in analyses. The lower end of the range for this variable, for participants who do experience at least 1 .6 g-force event during the observation period is 0. There is no upper limit to this variable.

7 Sample Size

Our initial protocol proposed to randomize 136 participants; however, this randomization goal did not account for attrition at the 1- and 6-month driving simulations—the source of our primary endpoints. When we reached a sample size of 136, we estimated how many additional participants would be required to achieve 136 participants with completed driving simulation data at 1- and 6-months post-training. The calculation suggested that we needed to recruit a randomized sample size of 152 to achieve 136 participants with 1- and 6-month simulator outcomes (primary endpoints). (See Section 16 for date of this protocol change).

8 General Analysis Considerations

8.1 Timing of Analyses

- The final analyses of the driving simulation data will be performed after the final randomized participant has completed their 6-month driving simulation assessment.
- The final analyses of the DriveCam data will be performed after both a) all events from all participants have been recorded and b) all events from all participants have been coded and resolved for any discrepancies.
- The final analysis will be performed on datasets compiled by [name], MA after having been documented as having been cleaned and finalized.

8.2 Analysis Populations

8.2.1 Full Analysis Population (or Intention to Treat or Modified Intention to Treat)

- All subject who were randomized.
- Driving simulation outcomes: All participants will have baseline driving simulation. Missing driving simulation data at the 1-month and 6-month timepoints will be assumed to be missing at random and handled using multiple imputation.
- Demographic characteristics: All participants who are randomized will be included in the report of demographic characteristics of the sample.

8.2.2 Per Protocol Population

- DriveCam outcomes: All participants who produce any DriveCam events during the period beginning at post-training through 1-year post-training. For any participants with missing DriveCam 'long-glance' data, data will be assumed to be missing at random and handled using multiple imputation.

8.2.3 Safety Population

All subjects who have a DriveCam installed in their car will be monitored for safety as described in 8.5 Interim Analyses.

8.3 Covariates and Subgroups

For all analyses:

- Driving experience: Defined as baseline date minus the date that the teen received their graduated or full unrestricted license. Computed in months.

Specific to driving simulation analyses:

- Driving runs: Included in order to be able to include primary outcomes from the two driving runs conducted at the baseline, 1-month post-training assessment, and the 6-month post-training assessment. Generalized estimating equation (GEE) analyses allowed driving simulation data from the two "runs" nested within each of the three "drive types" nested within each participant to be modeled as correlated response variable data, but main or interaction effects for "runs" were not of theoretical interest.

Specific to DriveCam analyses:

- To account for variability in the length of time the DriveCam camera was installed in each participants' automobile during the 1-year post-training period was included as a covariate in addition to months of driving experience as detailed above.

Supplemental Analyses (Requested by New England Journal of Medicine reviewers, editor, and/or statistical expert)

- Moderation Effects—These analyses are post-hoc; thus, effects (adjusted mean difference or relative risk and 95% CI) will be reported rather than significance testing. Note that the widths of confidence intervals are not adjusted for multiple comparisons and no definite conclusions can be drawn from these results.

- Medication status dichotomized based on whether the teen reported taking ADHD medication at any point during the 12-months of naturalistic driving.
- COVID-19 Sensitivity Analysis
 - For 56 (FOCAL+: n=29 teens; Control: n=27 teens) of the 152 participants, their 1-year of naturalistic driving included days beyond March 15, 2020 when COVID restrictions were put into place. We will conduct a sensitivity analyses of our naturalistic driving results by re-running our primary and secondary analyses but including only the 96 teens (FOCAL+ n=47; Control n=49) whose 1-year of naturalistic driving ended prior to COVID restrictions.

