b. Moderator analyses. We ran a moderator analysis examining age and medication status as moderators of FOCAL+ training effects. For the driving simulation outcomes, we examined whether the improvements from baseline to 1-month post-training and baseline to 6-months post-training were moderated by baseline age or medication status. We ran GEE models like those conducted for the primary analyses as described in 10.1 Primary Analysis, however we inserted the moderator variable in the model, analyzed a fully factorially crossed 4-way interaction model, but assessed the significance of the relevant 3-way interactions (Group x Drive Timepoint: baseline vs. 1-month; baseline vs. 6-months x [Moderator Variable]). For DriveCam outcomes, we examined whether group differences on long glances and crash/near-crashes were moderated by baseline age or medication status. We ran multi-level generalized linear mixed models with a logit link function similar to those conducted for the secondary analyses as reported in the manuscript, however we inserted the moderator variable in the model and assessed the significance of the 2-way interaction between Group x [Moderator Variable].

08/15/2022

The following statistical changes were made based on New England Journal of Medicine statistical expert and editor feedback.

1) Supplemental analyses were trimmed to analyses for which we could provide a strong rationale. Specifically, we will only report moderation analysis of the medication on training outcomes and COVID-19 sensitivity analyses.

a. Medication Moderation. For the driving simulation outcomes, we examined whether the improvements from baseline to 1-month post-training and baseline to 6-months post-training were moderated by medication status. These analyses were not intent-to-treat since only the 140 teens for whom we had information about medication status during the 1 year of follow-up were included in these analyses. Adjusted mean differences for standard-deviation of lane-position and natural logarithmic incident rate ratios for count of long glances were computed

using multiple group analysis methods. Specifically, conditional on months of driving experience, training group difference statistics were computed separately across binary medication status.

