For DriveCam outcomes, relative risk statistics for binary indicators of long glances and crash/near crash were computed conditional on both months of driving experience and days of DriveCam installation. Specifically, relative risk statistics were computed separately across binary medication status

b. COVID-19 Sensitivity. For 56 (FOCAL+: n=29 teens; Control: n=27 teens) of the 152 participants, their 1-year of naturalistic driving included days beyond March 15, 2020 when COVID restrictions were put into place. We conducted a sensitivity analyses of our naturalistic driving results by re-running our primary and secondary analyses but including only the 96 teens (FOCAL+ n=47; Control n=49) whose 1-year of naturalistic driving ended prior to COVID restrictions.

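### The retained medication moderation analysis reports separate effects for medicated and unmedicated teens, but not the difference between them, which is what measures moderation

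*Combined protocol and SAP*

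**What the plan says.** SAP section 8.3 lists moderation effects among the supplemental analyses requested during journal review. Its reporting rule is: "These analyses are post-hoc; thus, effects (adjusted mean difference or relative risk and 95% CI) will be reported rather than significance testing". It adds that the "widths of confidence intervals are not adjusted for multiple comparisons and no definite conclusions can be drawn from these results". The moderator is binary: "Medication status dichotomized based on whether the teen reported taking ADHD medication at any point during the 12-months of naturalistic driving".

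The 08/15/2022 entry in section 14.7 narrows the supplement: "we will only report moderation analysis of the medication on training outcomes and COVID-19 sensitivity analyses". For the simulator outcomes the question is whether improvements from baseline to 1 month and "baseline to 6-months post-training were moderated by medication status". The method given is that "training group difference statistics were computed separately across binary medication status", conditional on months of driving experience, in the 140 teens with known medication status. For the DriveCam outcomes, "relative risk statistics were computed separately across binary medication status".

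Section 8.3 does not itself say that effects are computed by stratum; that detail is in 14.7. The two places are consistent, and neither names an interaction, a difference of differences or a ratio of ratios.

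**The concern.** The question is whether the training effect differs by medication status. The quantity that answers it is the difference between the two stratum effects: a difference in adjusted mean differences for SDLP, a ratio of incidence rate ratios for simulator glances, and a ratio of relative risks for each DriveCam outcome. The plan estimates the two components and stops there.

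Declining to test does not require this. Section 8.3 replaces tests with effects and 95% CIs, and a contrast with a 95% CI fits that rule.

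At stake is how the supplement will be read. Splitting 140 teens leaves each stratum with modest power, so one interval may exclude no effect and the other include it when nothing differs between the strata. A reader shown only the two intervals could take that pattern for moderation.

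**Working it through.** **Inputs from the documents.** 140 teens (SAP 14.7, 08/15/2022 entry); 1:1 randomization (SAP 6.3); effect sizes of .6 for FOCAL+ and .10 for sham, a net difference of 0.5 SD (protocol 5.f.2.a.1); stated power of at least .80 at 41 per group and 99% at 68 per group (same section).

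**Assumptions.** 70 teens per arm; medicated share 50-80% (not given); a continuous outcome at one time point; the same true effect d in both strata.

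**The protocol's own power figures.** A two-sided 5% two-sample t-test at one visit with d = 0.5 gives 61% at 41 per group and 83% at 68. With d = 0.6 it gives 77% and 94%. The stated figures come from a Monte Carlo simulation of a main effect over repeated visits. Averaging k visits with correlation ρ scales the SD by √((1+(k−1)ρ)/k). With k = 5, d = 0.5 and ρ = 0.3, power (normal approximation) is 93% and 99%; with k = 5, d = 0.6 and ρ = 0.6, it is 91% and 99%. The correlation is not given, so the stated figures are neither confirmed nor refuted. Because they imply more precision than the single-visit model, I also used the effective d behind 99% power at 68 per group: (1.960 + 2.326) × √(2/68) = 0.735.

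**Chance of discordant intervals with identical effects.** Let p1 and p2 be the power in each stratum (noncentral t, two-sided 5%, n per arm = 70 × share). The strata contain different teens, so

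P(exactly one CI excludes no effect) = p1(1 − p2) + p2(1 − p1).

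- 50:50, d = 0.5: n = 35 and 35 per arm; p1 = p2 = 0.541; 2 × 0.541 × 0.459 = 0.497.
- 70:30, d = 0.5: n = 49 and 21 per arm; p1 = 0.688, p2 = 0.353; 0.688 × 0.647 + 0.353 × 0.312 = 0.555.

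| True d in both strata | 50:50 | 70:30 | 80:20 |
|---|---|---|---|
| 0 | 9.5% | 9.5% | 9.5% |
| 0.3 | 36% | 37% | 39% |
| 0.5 | 50% | 56% | 63% |
| 0.6 | 42% | 52% | 63% |
| 0.735 | 24% | 37% | 53% |

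A simulation with 40,000 replicates, run for d = 0, 0.5 and 0.735, agrees to within a few points. The largest gap is at d = 0.735 and 80:20: 50% against 53%.

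**The direct contrast.** In the same simulation, the 95% CI for the difference between stratum effects excluded zero in 5.1-5.8% of replicates.

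**Precision of the contrast.** Half-width = 1.96 × √(2/n1 + 2/n2), with n1 and n2 per arm in each stratum:

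- 50:50: 1.96 × √(2/35 + 2/35) = 0.66 SD
- 70:30: 1.96 × √(2/49 + 2/21) = 0.72 SD
- Overall effect in 140 teens, for comparison: 1.96 × √(2/70) = 0.33 SD

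At 50:50 the contrast has 80% power only for a difference of (1.960 + 0.842) × √(4/35) = 0.95 SD, and about 32% power for a difference of 0.5 SD.

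**The case against.** The strongest reply is that the SAP never proposes to call moderation when one interval excludes no effect and the other does not. Section 8.3 rules out significance testing and says no definite conclusions can be drawn. That wording covers any inference, not only multiplicity. This stands: the percentages describe a reading the layout invites, not a rule in the plan.

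The numbers also depend on unstated quantities. A reader might infer that identical effects would look moderated about half the time. The documents do not support a fixed rate, because the medication split is not given and the result runs from about 10% to 63% over the values tried. Nor do they support a larger figure accumulated over the four simulator comparisons. At an assumed correlation of 0.5 and splits of 50:50 and 70:30, that figure is 89-91% at d = 0.5 but 53-68% at d = 0.735. The model is also for a continuous outcome, whereas simulator glances are counts and the DriveCam outcomes are binary events clustered within teens.

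A reader might further infer that the analysis cannot answer its question. That is too strong. Because the strata are different teens, an approximate contrast follows from the two estimates and their CIs (on the log scale for ratios). It is unreported, not unrecoverable.

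Finally, the 06/23/2022 entry, which "assessed the significance of the relevant 3-way interactions" for the simulator outcomes, is superseded, so the absence of those terms now is not in itself an error. It shows only that a contrast is feasible. Protocol section 5.f.2.c likewise planned an intervention-by-moderator term, for other moderators.

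What the reply leaves untouched is that the named statistics do not include the one that measures moderation.

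**Conclusion.** The point holds as a minor reporting improvement. The current text asks about moderation and names only stratum-specific effects. With identical true effects, comparing whether each interval excludes no effect would mislead about 10% of the time with no effect, 36-63% for d = 0.3-0.6, and 24-53% at d = 0.735, against about 5% for the direct contrast. These figures rest on 140 teens in equal arms, one continuous comparison, and an assumed 50-80% medicated.

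The analysis is post hoc, its simulator part is stated not to be intent-to-treat, and no primary or secondary endpoint result is affected. The SAP's disclaimer limits the harm but does not supply the missing estimate.

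**What to change.** In section 8.3, after the reporting rule, add wording such as:

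> For each outcome we will report the effect in each medication stratum and, as the moderation estimate, the between-stratum contrast with its 95% CI: the difference in adjusted mean differences for SDLP, the ratio of incidence rate ratios for simulator glances, and the ratio of relative risks for each DriveCam outcome. No p-values will be given. Statements about moderation will rest on this contrast and not on whether either stratum's interval excludes no effect.

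Keep the post-hoc label and the statement that no definite conclusions can be drawn.

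The cost is a sentence or two of SAP text and one extra contrast per outcome and, for the simulator outcomes, per time point. No new data are needed. The downside is a wide interval (about ±0.66 SD at 50:50 and ±0.72 SD at 70:30), which will show that these data say little about moderation.

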5.1 Study Objectives

The goal of the proposed research is to empirically test the effectiveness of the FOCAL+ intervention in comparison to a sham intervention at improving visual attention and driving performance in teens with ADHD. Specifically, we will conduct a randomized controlled trial using 152 teens diagnosed with ADHD. Teens will be randomized to receive 5 training sessions of the FOCAL+ intervention or a sham intervention. 1-month and 6-months post-training, teens' driving skills, including frequency of extended eye glances, will be assessed during driving simulation. In addition, at the conclusion of training, a DriveCam camera system in their car will record naturalistic driving. The DriveCam will remain in their car until 12-months post-training. Finally, we will acquire the teen's driving records for the period they are in the study.

Primary Objective: We will examine the effectiveness of the FOCAL+ intervention versus sham intervention at decreasing rates of extended glances away from the roadway and improving driving performance among teens with ADHD at 1-month post-training, and 6-months post-training.

Secondary Objective: We will examine the effectiveness of the FOCAL+ intervention versus sham intervention in decreasing rates of extended glances away from the roadway, frequency of driving events, crashes, and crashes/near crashes as measured by in-car technology (DriveCam) during the 12-months post-training.

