- (3) conduct FOCAL+, and sham intervention trainings (5-sessions, 1 week apart),
- (4) conduct driving simulation assessments at baseline, 1-, and 6-months post-training,
- (5) collect information about medication use at baseline, 6-months, and 12-months post-training,
- (6) install and collect driving data using DriveCam cameras,
- (7) collect driving records,
- (8) conduct data entry and coding.

Since we forecast that recruitment will take 4 years to complete, we expect that some post-intervention data collection will continue into Year 05. However, most of Year 05 will be devoted to data cleaning, analyses, and preparation of study findings for publication and dissemination.

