9.6 Derived variables

- **Participant Age:** (moderator for supplemental analyses). Age will be measured in years (using decimals; range 16.00-19.99) and will be calculated by subtracting the participant’s date of baseline visit from their date of birth
- **Stimulant medication status:** dichotomized based on whether the teen reported taking ADHD medication at any point during the 12-months of naturalistic driving.

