11.7 Prior and Concurrent Medications

A medication interview conducted with the teen and parent that captures current prescribed medication usage and past prescribed medication usage for attention, learning, emotional, or behavioral difficulties since driving. This questionnaire will be administered during the in-person visits at Baseline and 6-months. In addition, this questionnaire will be sent as a REDCap survey for teens to complete at the 12-month time point.

The summary statistics for who was taking stimulant medication at baseline and during the 1-year of naturalistic driving for the whole sample and separately for each intervention will be produced.

12 Reporting Conventions

P-values ≥ 0.001 will be reported to 3 decimal places; p-values less than 0.001 will be reported as “<0.001”.

13 Quality Assurance of Statistical Programming

All primary analyses will be performed in SPSS (version 27) and SAS (version 9.4) using the generalized linear model function. All secondary analyses will be performed using *Mplus* (version 8.8) and SAS (version 9.4) on a Windows operating system. All analyses will be performed by [name]. All analyses code and results will be double-checked by [name].

14 Summary of Changes to the Protocol and/or SAP

The changes from the protocol-specified definitions of aims, outcomes and statistical analytic approaches are outlined below. Changes to the study procedures are also included here. These changes reflect 1) budget cuts that impacted our study design and 2) advances in our knowledge and experience with research methods in recruiting adolescents with ADHD, driving, and human factors.

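### The one retained moderation analysis splits the simulator outcomes by ADHD medication use reported after randomisation; a baseline split is available, and the SAP should use it or label the current one

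*Combined protocol and SAP*

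**What the plan says.** SAP 8.3 (Supplemental Analyses) gives the moderator as: "Medication status dichotomized based on whether the teen reported taking ADHD medication at any point during the 12-months of naturalistic driving". Section 9.6 repeats the definition, "dichotomized based on whether the teen reported taking ADHD medication at any point during the 12-months of naturalistic driving", but names the variable stimulant medication status.

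The 08/15/2022 entry in 14.7 cuts the supplemental work to this moderator and a COVID-19 sensitivity analysis. For the simulator, "we examined whether the improvements from baseline to 1-month post-training and baseline to 6-months post-training were moderated by medication status". It adds that these analyses are not intent-to-treat because "only the 140 teens for whom we had information about medication status during the 1 year of follow-up were included in these analyses". For DriveCam, "relative risk statistics were computed separately across binary medication status".

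The naturalistic year follows training. Section 5.1 starts recording when training ends and states: "The DriveCam will remain in their car until 12-months post-training". Under 6.3, the randomisation envelope is opened at the first training visit.

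Medication use is also recorded before randomisation. The study timeline in 6.1 plans to "collect information about medication use at baseline, 6-months, and 12-months post-training", and 11.7 says of the medication interview: "This questionnaire will be administered during the in-person visits at Baseline and 6-months". Section 9.8 lists stimulant use at baseline and during the post-training year among the summaries by group.

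Section 8.3 does carry cautions: the analysis is post-hoc, effects and intervals replace significance tests, the intervals are not adjusted for multiplicity, and no definite conclusions can be drawn.

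**The concern.** A subgroup fixed before randomisation keeps the randomised comparison inside each stratum. A subgroup defined by what happens after allocation need not: if training affects who takes or reports medication, the arms within a stratum may no longer be alike.

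Timing makes this sharper for the simulator. A teen who starts medication in month 9 counts as a user when the month-1 drive is analysed. Concurrent use is also a weak reason for the split here, because 6.1 tells teens who take stimulants to be off ADHD medication at the post-intervention assessments.

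At stake is the reading of the only moderation result the SAP retains. A reader could take a difference between users and non-users as effect modification when part of it reflects how the strata were formed.

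**Working it through.** **1. Order of events (6.3, 6.4; days counted from training 5).** Allocation is revealed at training 1. The 1-month window is days 30-45, the 6-month window is days 180-195, and the 12-month survey is nominally day 360. A yes can be settled at the 6-month interview. A no, or a start after month 6, is settled only at the survey:
- after the 1-month drive: 360 − 45 = 315 to 360 − 30 = 330 days
- after the 6-month drive: 360 − 195 = 165 to 360 − 180 = 180 days

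**2. Teens left out.** 152 − 140 = 12, and 12/152 = 7.9%.

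**3. What produces bias.** The inputs here are assumed: a true effect of −0.5 SD in every teen, so no real moderation, and a latent severity that correlates 0.3-0.5 with the outcome and also raises medication use. A simulation gave:
- arm does not affect use: both stratum effects stay near −0.50 SD
- training lowers the log-odds of use by 0.5-1.0: both effects shrink to about −0.41 to −0.48 SD, with almost no difference between strata
- training also changes which teens use medication: a false difference of about 0.11-0.24 SD

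So an arm effect on the amount of use can bias the stratum effects, but a false difference between strata needs the driving-medication relation to differ by arm.

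**4. Illustrative size for lane-position variability (SDLP).** Assumed: a proportion b = 40% or 60% use medication at baseline, and s = 10% or 20% of the rest start later. Starting follows a normal latent score that correlates r = 0.3 with worse follow-up driving in sham and 0 in FOCAL+.

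The mean latent score of starters is φ(t)/s, which is 1.755 at s = 10% and 1.400 at s = 20%. Worked case, b = 40% and s = 10%:
- starters are 0.6 × 0.1 = 0.06 of teens; user share p = 0.46
- sham users shift by (0.06/0.46) × 0.3 × 1.755 = +0.069 SD
- sham non-users shift by −0.3 × 1.755 × 0.1/0.9 = −0.059 SD
- FOCAL+ strata do not shift, so users minus non-users = −(0.069 + 0.059) = −0.13 SD

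On change from baseline, multiply by (1 − ρ), where ρ is the baseline-to-follow-up correlation: −0.064 at ρ = 0.5. The value ρ = 0.8 is the SDLP test-retest figure in protocol 5.e.1; using it for this simulator is an assumption.

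The standard error of the between-strata contrast with 140 teens, equal arms and no adjustment is √(4/(140p) + 4/(140(1 − p))) on levels. On change it is multiplied by √(2(1 − ρ)), which is 1 at ρ = 0.5 and 0.632 at ρ = 0.8.

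| b, s | p | Levels: false difference / SE | Change, ρ = 0.5 | Change, ρ = 0.8 |
|---|---|---|---|---|
| 40%, 10% | 46% | −0.13 / 0.339 = 38% | −0.064 / 0.339 = 19% | −0.026 / 0.215 = 12% |
| 40%, 20% | 52% | −0.20 / 0.338 = 59% | −0.102 / 0.338 = 30% | −0.041 / 0.214 = 19% |
| 60%, 10% | 64% | −0.09 / 0.352 = 26% | −0.046 / 0.352 = 13% | −0.018 / 0.223 = 8% |
| 60%, 20% | 68% | −0.15 / 0.362 = 41% | −0.078 / 0.362 = 22% | −0.031 / 0.229 = 14% |

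The entries come from a simulation of 4 million teens per arm; the hand calculation reproduces the first row to rounding.

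**5. Sensitivity (change scale).** The false difference roughly halves if r in FOCAL+ is 0.15. Its sign reverses if starting depends on baseline driving only. It is 0.06-0.20 SD if starting depends on the change itself. It is 0 within simulation error if selection is equal in both arms or the split uses baseline status.

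**6. Which scale applies.** The 14.7 entry of 08/15/2022 speaks of improvement from baseline. Section 10.5 builds adjusted means from intercepts, and the 06/23/2022 entry reports adjusted mean differences at 1 and 6 months. Those two point to post-training levels for SDLP. Long glances are reported as rate ratios, which an SD scale does not describe.

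**The case against.** Much is already disclosed. The definition states its own window, 8.3 says post-hoc with no definite conclusions, 14.7 says not intent-to-treat, and 11.7 provides stimulant use by arm. The analysis is supplemental and was requested during journal review. Under 6.3, participants do not know which training is active, so arm-dependent medication use is less likely. For DriveCam the follow-up definition has a rationale: protocol 5.f.2.a planned medication as a time-varying covariate, and self-report replaced daily monitoring after the budget cut.

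Most of this stands, and it limits the point. It does not remove it. Post-hoc describes when the analysis was chosen, not when the strata were formed; a post-hoc split on baseline status would keep the randomised comparison. Not intent-to-treat is explained by the teens with missing information. The by-arm table is a partial safeguard only: in step 4 the user share is the same in both arms, yet a false difference appears.

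Three stronger readings are tempting and are not supported:
- **The moderation result is biased.** The documents give no data showing that training changed medication use or who used it.
- **Any dependence of use on arm and on driving creates false moderation.** Step 3 shows that it need not.
- **The efficacy conclusions are affected.** Medication status does not enter the primary or secondary models.

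**Conclusion.** The point holds as a minor one. The SAP's only retained moderator is measured after randomisation and is partly settled after the simulator outcomes it divides; neither 8.3 nor 14.7 says so, and the documents give no reason for passing over baseline use. These facts are certain; harm is not. The size is unknown. In the main scenario the false SDLP difference stays below one standard error: about 26-59% on post-training levels, the likelier reported scale, and 8-30% on change. Those figures rest on assumed start rates, correlations and treatment effect, and say nothing about the long-glance rate ratios.

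**What to change.** - **Simulator outcomes (8.3 and 9.6).** Define the moderator as current prescribed ADHD medication use, yes or no, at the baseline interview. The word *current* is needed because 11.7 records both current and past use. Include every randomised teen with a baseline report. Use one term throughout, *ADHD medication* rather than *stimulant*.
- **Existing simulator split.** Section 14.7 is written in the past tense, so results already exist. If the follow-up split is still shown, put it beside the baseline split and label it *post-randomisation, descriptive*.
- **DriveCam outcomes.** Keep the follow-up split with the same label, and report the baseline split beside it.
- **Unchanged.** The primary and secondary analyses and the imputation models in 8.4.

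The cost is some SAP wording and a small re-run of a supplemental analysis, with no new data. There are two drawbacks. The baseline split is a further post-hoc choice and should be disclosed as one. Baseline status is also a less exact marker of medication use during naturalistic driving, which is why the labelled follow-up split may stay for DriveCam. Some of the 12 omitted teens may be recovered; how many depends on the completeness of baseline reports, which the documents do not state.
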